**2. EXTERNAL IRB REVIEW HISTORY\***

N/A

**3. PRIOR APPROVALS:**

Wilderness Medicine Society (WMS) – Study grant pending

Nepal Health Research Council (NHRC) – pending. NHRC generally requires outside institutional IRB approval before they will give final approval. Once final approval is obtained, it will be uploaded.

**4. OBJECTIVES\***

The overall goal of this study is to detect preclinical signs of HAPE by lung ultrasonography and evaluate the effectiveness of acetazolamide at decreasing pulmonary edema by using ultrasound.

**5. BACKGROUND\***

See attached WMS grant proposal page 2-3

**6. INCLUSION AND EXCLUSION CRITERIA\***

Inclusion criteria: 1.) At least 18 years of age; 2.) Able to consent; 3.) English speaking; 4.) Trekking directly to Everest Base Camp

Exclusion criteria: 1.) Age less than 18 years; 2.) Non-English speaking; 3.) Pregnant; 4.) Already had a diagnosis of acute mountain sickness, high-altitude cerebral edema, or HAPE 5.) Had been on a high-altitude trek 2 weeks prior to this study 6.) Has taken acetazolamide 1 week prior to start of trek 7.) Has a sulfa allergy 8.) Has any type of acute or chronic pulmonary conditions

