**9. STUDY TIMELINES\***

**H00014860 Acetazolamide on High-Altitude Pulmonary Edema**  
**Version 2 – 02/10/2018**  
**INVESTIGATOR STUDY PLAN**

We will recruit subjects from the 2018 Wilderness Medical Society (WMS) Everest Base Camp Trek. The WMS 2018 Everest Base Camp Trek is a trekking trip from Lukla, Nepal (2840m) to Everest Base Camp (5400m) in Spring 2018. The duration of the trek is approximately 3 weeks. The duration of enrollment will be approximately 1-2 days during preparation part of the trip in Kathmandu, Nepal at the beginning of the trek. The estimated date for completion of primary analyses will be December 2018.

WMS Everest Base Camp Trek Itinerary

March 25	Arrival in Kathmandu, transfer to hotel (1310m)
March 26	Sightseeing in Kathmandu and preparation day **Enrollment day**
March 27	Fly to Lukla (2840m), trek to Phakding (2610m)
March 28	Trek to Namche (3440m) **Data Collection 1**
March 29	Namche and slow walk to Kunde Hospital/Kumjung
March 30	Extra day in Namche and visit Namche Bazar (3440m)
March 31	Trek to Tengboche (3860m)
April 1	Trek to Pheriche (4270m) **Data Collection 2**
April 2	Pheriche / hike Nakarsang Hill (5200m)
April 3	Pheriche
April 4	Lobuche (4910m) **Data Collection 3**
April 5	Gorakshep (5140m)
April 6	Hike to Kalapathar (5550m) / Everest Base Camp (5364m)
April 7	Everest Base Camp (5364m) **Data Collection 4 & 5**
April 8	Pheriche
April 9	Khumjung (3760m)
April 10	Manjo (2835m)
April 11	Lukla(2840m)
April 12	Fly back to Kathmandu
April 13	Kathmandu farewell dinner **Data Collection 6**
April 14	Final departure to home

\* May change slightly depending on weather, conditions, etc.

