**10. STUDY ENDPOINTS\***

Primary outcome measures: 1.) Pulmonary edema detected in lung ultrasound exams before and after taking acetazolamide.

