### 11. PROCEDURES INVOLVED\*

After informed consent has been obtained, subjects will be randomized to receive either of the study medications medication: 250mg of acetazolamide or a placebo pill. Investigator will be blinded as to which arm of the study the patient is enrolled. Medications will be obtained from the UMass Pharmacy in individual blister packs. We will ensure that acetazolamide and the chosen placebo pill look similar. Any identifying information on the blister pack will be obscured by a black marking pen, if necessary. Medications will then be inserted into small opaque envelopes and marked with only a number. Numbers will be assigned to medications by use of the random number generator function (=RANDBETWEEN(1,30\*)) (\*The final number will depend on the total number of subjects) in Excel with the top half of the list being assigned Acetazolamide and the bottom half placebo pill. The list will then be sorted in numerical order in Excel. When a subject enrolls, a number will be assigned in order. Blinding of the numbers and assigned medications as well as the assembly of the envelopes will be done prior to leaving UMass by PI's faculty advisor who will not be involved in medication administration.

At each of the time points noted in #9, lung ultrasound exams will be done at bedside in a private location to measure the total ultrasound lung comets (an ultrasound finding for pulmonary edema) for a "comet score." One (1) single dose of 250mg acetazolamide or placebo will be given at Everest Base Camp (Data Collection #4) and a comet score will be measured again 12 hours after acetazolamide or placebo is given. Previous studies have shown that comet scores increase with altitude and given that Everest Base Camp is the highest altitude the subjects will be residing at, it is believed that we will find the biggest decrease in comet score if acetazolamide is given at this point. The subject's heart rate and oxygen saturation will also be collected via a pulse oximeter.

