## **H00014860 Acetazolamide on High-Altitude Pulmonary Edema**

**Version 2 – 02/10/2018**

### **INVESTIGATOR STUDY PLAN**

In the case that ultrasound imaging picks up findings that could indicate that subject is at risk of developing high-altitude pulmonary edema, in addition to any subject displaying signs of severe altitude illness, they will be treated and evacuated as determined necessary by the WMS medical providers present. The 2018 WMS trip leaders are Emergency Physicians who are trained in wilderness medicine and have substantial experience diagnosing and treating altitude illness and arranging evacuations in Nepal. Participants requiring evacuation will be accompanied by a guide. In the event that an individual cannot descend on foot, helicopter evacuation is possible up to Everest Base Camp. All WMS trip participants are required to carry evidence of Evacuation and Medicine Travel insurance that covers high altitude. Participation in this research project will not dictate or change treatment or evacuation in any way.

This study involves no more than minimal risk to subjects, and therefore will not utilize a DSMB.

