**19. MULTI-SITE RESEARCH\***

This study is being conducted simultaneously with study #H00014129. While the studies are on the same subjects, the studies are expected to minimally impact each other. The main potential effect the studies could have on each other is the time that will take for each to be completed at a time point, however neither data collection is expected to take more than 20 minutes per subject. The pulmonary ultrasound measurements of study #H00014860 are short duration and not expected to impact cognitive function or the ability of subjects to answer questions on the concussion software. The concussion apps in this study do not require physical exertion except minimal effort during a short time standing and balancing and are not expected to impact pulmonary edema or the ultrasound measurements.

Study #H00014860 involves a single dose of acetazolamide or placebo at Everest Base Camp. The concussion app data for this time point will be collected before the medication is given and therefore should not be impacted. An additional data point 12 hours later at Everest Base Camp will be added to assess any effect of the medication on the concussion app data for study #H00014129. While this study's main goal is not to assess the effect of acetazolamide on the cognitive functions measured by the concussion apps, it may add useful information both for this study and for study #H00014860. The half-life of immediate release acetazolamide is 5-6 hours and is expected to have been excreted prior to the next time point six days later after descent.

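### Off-study acetazolamide near the April 7 dose is neither restricted nor recorded in the visible text, and section 13 has no analysis for it, so the DC4-DC5 arm contrast could be diluted by an unknown amount

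*Combined protocol and SAP*

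**What the plan says.** - Section 6, exclusion 6, is the only visible rule on non-study acetazolamide: "Has taken acetazolamide 1 week prior to start of trek".
- Section 9 puts enrolment in Kathmandu: "The duration of enrollment will be approximately 1-2 days during preparation part of the trip in Kathmandu, Nepal at the beginning of the trek". The itinerary has enrolment on March 26, the flight to Lukla and first walking day on March 27, and DC4 and DC5 at Everest Base Camp on April 7. Dates may shift slightly.
- Section 10 gives the primary outcome as "Pulmonary edema detected in lung ultrasound exams before and after taking acetazolamide". Section 11 places the single dose of drug or placebo at DC4, and "a comet score will be measured again 12 hours after acetazolamide or placebo is given".
- Section 14 says that subjects with worrying ultrasound findings or severe altitude illness will be cared for by the trip's providers: "they will be treated and evacuated as determined necessary by the WMS medical providers present". It adds: "Participation in this research project will not dictate or change treatment or evacuation in any way".
- Section 32 describes the drug as approved for acute mountain sickness and recommended by guidelines for preventing HAPE.
- Section 19 states: "The half-life of immediate release acetazolamide is 5-6 hours".
- The data named in sections 11, 16 and 26 are demographics, heart rate, oxygen saturation and images. Section 26 also mentions a data collection sheet, which is not in the file.
- Section 13 lists Fisher's exact test for categorical variables, a paired t-test for continuous ones, and regression of comets on vital signs. Off-study drug does not appear.

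**The concern.** The trial asks whether one blinded tablet at DC4 changes the comet score by DC5. A subject who already has acetazolamide on board at DC4, or who takes some between DC4 and DC5, may show less difference between drug and placebo than an unexposed subject. If so, the arm difference is pulled toward zero. If use is not written down at the time, nobody can later judge whether a null result reflects the drug or the background exposure.

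The protocol already treats this exposure as relevant. It excludes pre-trek users, and section 19 uses the half-life to argue that the study dose will have cleared before the next visit. It does not apply that reasoning to drug taken shortly before DC4.

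Section 13 adds to the difficulty. The only test it names for a continuous score is paired. That describes change within subjects and does not compare the arms, so the plan has no stated between-arm contrast of the comet score to which a sensitivity analysis could be attached.

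**Working it through.** **1. Does exclusion 6 reach the dose?** March 27 to April 7 is 11 days, or 264 h (12 days from enrolment). In half-lives: 264/6 = 44 to 264/5 = 52.8. Drug taken before the trek is gone by DC4, so the criterion neither helps nor harms this comparison.

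**2. Which off-study use could matter?** Fraction remaining = 0.5^(hours / half-life), for half-lives of 5 h and 6 h:

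| Last tablet before DC4 | Half-lives | Remaining |
|---|---|---|
| 72 h (DC3, April 4) | 12-14.4 | 0.005-0.02% |
| 48 h | 8-9.6 | 0.1-0.4% |
| 24 h | 4-4.8 | 4-6% |
| 12 h | 2-2.4 | 19-25% |

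Only use shortly before DC4, ongoing use, or use between DC4 and DC5 is of interest.

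**3. The plan's own figure.** Section 13 gives 14 subjects for 80% power without an effect size or SD, so it cannot be reproduced. Solved backwards (two-sided 0.05, noncentral t), 14 implies a standardised effect d of 1.63 if it means 7 per arm, 1.10 if 14 per arm, and 0.81 if 14 pairs. The illustration uses d = 1.63.

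**4. Illustration.** Assumptions, none from the documents: N = 20 (the low end of the expected 20-30), 10 per arm, 4 users placed at random, SD of change 1, no mean change on placebo, and a two-sample t-test on DC4-DC5 change. A user on active drug loses a fraction L of the effect. The expected arm difference is then d × (1 − 0.2 × L), since 4/20 = 0.2. Power with users kept in is simulated:

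| L | Expected difference | Power, users kept in |
|---|---|---|
| no users | 1.63 | 93% |
| 6% | 1.63 × 0.988 = 1.61 | 93% |
| 25% | 1.63 × 0.95 = 1.55 | 90% |
| 50% | 1.63 × 0.90 = 1.47 | 86% |
| 75% | 1.63 × 0.85 = 1.39 | 79% |
| 100% | 1.63 × 0.80 = 1.30 | 71% |

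With the 4 users left out, 16 subjects remain and power is 85% whatever L is. The two approaches cross at about L = 50%.

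**5. Sensitivity to the meaning of 14.** At L = 100% with 4 users in 20, power without users, with users kept in, and with users left out is 64%, 43% and 53% for d = 1.10, and 40%, 26% and 32% for d = 0.81. The unstated basis of the 14 moves power at least as much as the users do.

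**The case against.** **Exclusion 6 is not wrong.** A reader might infer that it is anchored to the wrong date. It is not: it is applied in Kathmandu, and no entry criterion can screen tablets taken days later. It should stay. The gap lies in what happens between entry and DC5.

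**The absence of recording cannot be confirmed.** The data collection sheet, consent form, recruitment email and grant proposal are not in the file, and any of them might record or restrict use. This stands, and it makes the recording request conditional. The silence of section 13 can be verified.

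**Use may be rare.** No passage says how many trekkers take the drug. The treatment sentence in section 14 concerns HAPE risk and severe illness, and section 15 lets very ill or evacuated subjects be withdrawn, so some treated subjects would never reach DC4. This also stands. Sections 14 and 32 make use plausible; they do not make it common.

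**Leaving users out need not help.** A reader might infer a clear power gain from dropping recent users. That holds only if they lose most of the contrast. If the loss merely tracked residual drug (25% at 12 h, 6% at 24 h), keeping them would give 90% to 93%, against 85% without them.

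**Imbalance is easily overstated.** With 4 users in two arms of 10, the arms differ by 2 or more users with probability 58%, but that only means any split other than 2-2. A 4-0 split has probability 8.7%. In the model above, imbalance varies the attenuation and cannot inflate the expected effect, so the calculation gives no support for a distortion in either direction.

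**Use after enrolment follows randomisation.** Numbers are assigned at enrolment, so use during the ascent is a pre-dose variable only while the blind holds. Section 11 has the faculty advisor prepare the coded envelopes, and section 23 has the same advisor on the trek. Section 11 keeps the advisor out of administration, but the condition has to be stated.

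**Conclusion.** The concern holds in a limited form. Exclusion 6 cannot protect a comparison made 11 days after trek start. The visible text neither restricts nor records later use, section 14 leaves treatment untouched by participation, and section 13 has no analysis for such use and no named between-arm test of the comet score. Recent or ongoing use could therefore dilute the DC4-DC5 contrast with no means of examining it.

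The size is unknown. In the illustration the loss of power runs from almost nothing (93%) to 22 points (93% to 71%). It rests on an assumed 4 users in 20, an assumed loss per user and one of three readings of the 14. Use before the blinded dose is balanced between arms in expectation, so the expected effect is attenuation, not systematic bias. The documents do not show that dilution will occur. The change is worth making because it is cheap and because use not recorded on the trek can later be recovered only from memory.

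**What to change.** 1. **Section 11.** Unless the data collection sheet already does so, record off-study acetazolamide (yes/no, last date and time) at each data collection through DC5.
2. **Section 13, primary analysis.** Compare DC4-DC5 change between arms in all randomised subjects who have both scores, whatever their off-study use. Report by arm those withdrawn before DC4 or DC5.
3. **Section 13, sensitivity analysis.** Prespecify one analysis that leaves out subjects with recorded use in a stated window before the DC4 dose (48 h, for example, is 8 to 9.6 half-lives). Describe it as use before the blinded dose, valid only while the blind holds, and read it for attenuation and not as a gain in power. Report use between DC4 and DC5 by arm, descriptively, excluding nobody for it.

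Exclusion 6, the allocation and the envelopes stay as they are. The cost is one self-reported item at visits already planned and a few sentences of text. The downsides are imperfect recall of the last tablet and a smaller sensitivity set (16 of 20 in the illustration).

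Whether off-study use is allowed, and who is dosed at DC4, is for the investigators to settle by reconciling sections 6, 11, 14 and 15. No rule is proposed here.

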**7. STUDY-WIDE NUMBER OF SUBJECTS\***

N/A

**8. STUDY-WIDE RECRUITMENT METHODS\***

N/A

**9. STUDY TIMELINES\***

**H00014860 Acetazolamide on High-Altitude Pulmonary Edema**  
**Version 2 – 02/10/2018**  
**INVESTIGATOR STUDY PLAN**

We will recruit subjects from the 2018 Wilderness Medical Society (WMS) Everest Base Camp Trek. The WMS 2018 Everest Base Camp Trek is a trekking trip from Lukla, Nepal (2840m) to Everest Base Camp (5400m) in Spring 2018. The duration of the trek is approximately 3 weeks. The duration of enrollment will be approximately 1-2 days during preparation part of the trip in Kathmandu, Nepal at the beginning of the trek. The estimated date for completion of primary analyses will be December 2018.

WMS Everest Base Camp Trek Itinerary

March 25	Arrival in Kathmandu, transfer to hotel (1310m)
March 26	Sightseeing in Kathmandu and preparation day **Enrollment day**
March 27	Fly to Lukla (2840m), trek to Phakding (2610m)
March 28	Trek to Namche (3440m) **Data Collection 1**
March 29	Namche and slow walk to Kunde Hospital/Kumjung
March 30	Extra day in Namche and visit Namche Bazar (3440m)
March 31	Trek to Tengboche (3860m)
April 1	Trek to Pheriche (4270m) **Data Collection 2**
April 2	Pheriche / hike Nakarsang Hill (5200m)
April 3	Pheriche
April 4	Lobuche (4910m) **Data Collection 3**
April 5	Gorakshep (5140m)
April 6	Hike to Kalapathar (5550m) / Everest Base Camp (5364m)
April 7	Everest Base Camp (5364m) **Data Collection 4 & 5**
April 8	Pheriche
April 9	Khumjung (3760m)
April 10	Manjo (2835m)
April 11	Lukla(2840m)
April 12	Fly back to Kathmandu
April 13	Kathmandu farewell dinner **Data Collection 6**
April 14	Final departure to home

\* May change slightly depending on weather, conditions, etc.

**10. STUDY ENDPOINTS\***

Primary outcome measures: 1.) Pulmonary edema detected in lung ultrasound exams before and after taking acetazolamide.

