#### **13. Data Analysis and Management\***

Previous studies in lung ultrasonography suggest that a minimum of 14 subjects will be needed to provide 80% power to detect a statistically significant difference in ultrasound lung comets. Between 20-30 total subjects are expected.

For data analysis, Fisher's exact test will be used to compare categorical variables. Continuous variables will be analyzed with paired Student's t-test. Linear regression models will be used to assess correlations between ultrasound lung comets and vital signs. In all cases p values < 0.05 will be considered significant. Data will be reported as mean +/- SD

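### The primary outcome is worded as edema being detected, with no scale, cut-off or test attached, while the procedures and the power statement rest on a comet score

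*Combined protocol and SAP*

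**What the plan says.** - **Section 10 (Study Endpoints)** gives the whole definition of the primary outcome: "Pulmonary edema detected in lung ultrasound exams before and after taking acetazolamide". It states no unit, cut-off, named time points, change score or comparison between arms.
- **Section 11 (Procedures Involved)** describes a count. Lung comets, presented there as the ultrasound sign of pulmonary edema, are totalled into a comet score, and 28 images are recorded per session. After the single dose at Everest Base Camp, "a comet score will be measured again 12 hours after acetazolamide or placebo is given". The expected result is on the same scale: "it is believed that we will find the biggest decrease in comet score if acetazolamide is given at this point".
- **Section 13 (Data Analysis and Management)** states that "a minimum of 14 subjects will be needed to provide 80% power to detect a statistically significant difference in ultrasound lung comets", and adds: "Between 20-30 total subjects are expected". It assigns Fisher's exact test to categorical variables and a paired t-test to continuous ones, and does not say which kind the primary outcome is.
- **Section 21 (Sharing of Research Results)** says that definitive review of the images follows the trek.
- No section of the supplied text gives a comet score at which edema counts as present. Section 11 refers to an attached grant proposal for scanning methods, and that attachment is not among the documents.

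**The concern.** The outcome named in section 10 is not clearly the quantity that section 11 measures or that section 13 powers. Taken literally, detection is a present/absent outcome and leads to Fisher's test. Taken with sections 11 and 13, it is a count and leads to a t-test. The plan does not choose.

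Two things are at stake. First, a present/absent outcome uses less of the data. A subject whose score falls but stays above the cut-off counts as unchanged, and a subject below the cut-off at dosing cannot improve. That is a poor match to the fall in score that section 11 expects. Second, if the scale or the cut-off is settled only once scores and arms are known, the nominal 5% error rate no longer holds.

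**Working it through.** **The plan's own figure.** The 14 subjects for 80% power cannot be reproduced. Section 13 gives no effect size, SD, event rate or sidedness, and does not say whether 14 is the total or per arm. I therefore solved for the effect that makes it true.

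**Inputs from the plan:** 14 subjects and 80% power (section 13); 20-30 subjects expected, so 10-15 per arm; half the list to each arm (section 11); significance at 0.05 (section 13).

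**Assumptions:** two-sided test; normal outcome with equal SD; post-dose comparison between arms; present/absent obtained by cutting that same outcome.

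**Step 1. Effect implied for the count.** Power = P(T > t₀.₉₇₅), where T is noncentral t with 2n−2 degrees of freedom and noncentrality d√(n/2).
- 14 as total (n = 7 per arm): 80% power needs d = 1.63. Check: 1.63 × √3.5 = 3.05.
- 14 per arm: 80% power needs d = 1.10. Check: 1.10 × √7 = 2.91.

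**Step 2. Cut the outcome.** With the cut-off midway between the arm means, the proportions with edema are Φ(d/2) and Φ(−d/2): 79% against 21% for d = 1.63, and 71% against 29% for d = 1.10. A search over cut-offs confirms that the midpoint is the most favourable or within one percentage point of it. Fisher power is the sum of the product binomial probabilities over all tables with p ≤ 0.05.

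| Effect | Per arm | Count, t-test | Present/absent, midpoint | Cut at control median | Cut at control mean + 0.5 SD |
|---|---|---|---|---|---|
| 1.63 SD | 7 | 80% | 42% | 17% | 3% |
| 1.63 SD | 10 | 93% | 60% | 43% | 14% |
| 1.63 SD | 15 | 99% | 85% | 73% | 43% |
| 1.10 SD | 10 | 64% | 27% | 22% | 10% |
| 1.10 SD | 14 | 80% | 44% | 43% | 25% |
| 1.10 SD | 15 | 83% | 48% | 41% | 28% |

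At the midpoint cut-off, Fisher's test needs 13 per arm rather than 7 to reach 80% for d = 1.63, and 25 rather than 14 for d = 1.10.

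**Step 3. Before/after reading.** If 14 means 14 pairs, 80% for the paired t-test implies a mean change of 0.81 SD of the differences. Cutting at the midpoint and using an exact McNemar test (which the plan does not name), simulated power is about 35%, 25%, 12% and 6% for before/after correlations of 0.3, 0.5, 0.7 and 0.8.

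**Step 4. Choosing the cut-off afterwards.** With no true effect, taking the smallest Fisher p over all cut-offs gives p < 0.05 in about 9% of trials at 10 per arm and 15% at 15 per arm. Counting only results that favour acetazolamide gives about 4.6% and 7.7%, against a nominal 2.5%. Fisher's test at one fixed cut-off stays below 5%.

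**The case against.** The best defence is that this is loose wording and not a second endpoint. Section 10 never says present/absent, proportion or incidence. Section 4 speaks of decreasing edema, section 11 treats comets as its sign and expects the score to fall, and section 13 powers on comets. Fisher's test appears only in a general sentence about categorical variables. On that reading the primary outcome is the comet score before and after dosing. This largely stands: a reader might infer that the plan declares a yes/no endpoint, and the documents do not support that. What remains is that the only sentence defining the primary outcome does not name the score, and no test is tied to it.

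Two other stronger inferences also fail. One is that no edema threshold exists and that it will be picked after reading. A threshold could be in the grant proposal, section 11 blinds the investigator, and section 21 says when images are reviewed, not when a cut-off is set. The supportable statement is that the supplied text gives no threshold and does not rule out a late choice. The other is that dichotomising would halve power as a rule. At 15 per arm with 1.63 SD, the loss at the best cut-off is 14 points (99% to 85%).

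It is also fair to say that Steps 1 and 2 model a post-dose comparison between arms, whereas section 13 names a paired t-test. The paired version in Step 3 shows a larger loss, so the direction does not depend on that choice.

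**Conclusion.** The primary outcome is ambiguous, and its most literal reading does not match the quantity that is measured and powered. Read as present/absent, it has lower power than the count in every setting computed. At the most favourable cut-off the loss runs from 14 points (30 subjects, 1.63 SD) to about 38 points (80% to 42%, 14 subjects in total), and it is larger at poor cut-offs or in a before/after analysis with high correlation. These figures rest on a normal outcome and on effects back-solved from the 14-subject statement. Comet counts may be skewed, and the plan gives no data to check this.

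The false-positive range of about 9-15% is a worst case. It assumes a free search over cut-offs with arms known and counts significance in either direction. The plan does not exclude this, but nothing in it says it will happen.

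This should be corrected before any image is read. It is more than a missing detail, because the two readings lead to different tests and can give different conclusions from the same scans.

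**What to change.** Reword section 10 so that the primary outcome is the change in total comet score (sum over the 28 windows) from Data Collection 4, scanned before study drug, to Data Collection 5, 12 hours after study drug, compared between the randomised arms.

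In section 13, name one test for it: for example ANCOVA on the Data Collection 5 score adjusted for the Data Collection 4 score, or a two-sample t-test on the change. The between-arm comparison has to be written out, because the paired t-test now listed would allow a within-arm analysis of the same change.

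Make edema present/absent a descriptive secondary outcome, with a single comet-score cut-off stated in section 10 before any image is read. If the grant proposal already contains a cut-off, copy it in.

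The cost is protocol wording only. The scans, readings and subjects are unchanged.
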